7.2.2.3. Summaries of Laboratory Abnormalities

The following summaries (number and percentage of subjects) of laboratory abnormalities will be provided by treatment group (subjects categorized according to most severe abnormality grade):

- Treatment-emergent laboratory abnormalities
- Treatment-emergent Grade 3 and 4 laboratory abnormalities
- Treatment-emergent marked laboratory abnormalities

For all summaries of laboratory abnormalities, the denominator is the number of subjects with any nonmissing postbaseline value in the given study period. A listing of treatment-emergent Grade 3 or 4 laboratory abnormalities will be provided.

7.2.3. ALT Elevation

An ALT elevation is defined as serum ALT $> 2 \times$ baseline value and $> 10 \times$ ULN, with or without associated symptoms. Confirmed ALT elevation (ALT flare) is defined as ALT elevations at 2 consecutive postbaseline visits. All treatment-emergent ALT elevations including confirmed ALT elevations will be summarized for the double-blind phase. All treatment-emergent and nontreatment-emergent ALT elevations will be included in a listing.

7.3. Bone Safety Analyses

7.3.1. Bone Mineral Density (BMD)

For BMD analysis during the double-blind phase, any available on-treatment record on or prior to Open-label Study Day 14 will be included into the double-blind phase summary for those who enter the open-label phase after completion of the double-blind phase.

Percentage change from baseline in hip BMD and spine BMD will be summarized by treatment group and visit using descriptive statistics for subjects in the Hip and Spine DXA Analysis Sets, respectively.

Missing values for hip and spine BMD will be imputed using LOCF up to Week 96 for the analyses of percentage change from baseline. The last on-treatment postbaseline observation will be carried forward to impute the missing value. Baseline observation will not be carried forward.

Percentage change from baseline in observed hip and spine BMD will be analyzed similarly provided up to Week 96.

Observed BMD values will be used for all the analyses described below:

For each subject and each visit, the clinical BMD status will be defined for hip and spine BMD based on the corrected t-score in Table 7-1.

Table 7-1. Normal, Osteopenia, and Osteoporosis as Defined by T-score

Clinical Status	BMD T-score
Normal	t-score \geq -1.0
Osteopenia	$-2.5 \leq$ t-score $<$ -1.0
Osteoporosis	t-score $<$ -2.5

The number and percentage of subjects in each clinical BMD status (normal, osteopenia, and osteoporosis) will be summarized by visit and by baseline clinical status for both hip and spine.

For each subject and each visit, percentage change from baseline in hip BMD and spine BMD will be classified into 10 categories: $> 7\%$ decrease, $> 5\%$ to $\leq 7\%$ decrease, $> 3\%$ to $\leq 5\%$ decrease, $> 1\%$ to $\leq 3\%$ decrease, > 0 to $\leq 1\%$ decrease, 0 to $\leq 1\%$ increase, $> 1\%$ to $\leq 3\%$ increase, $> 3\%$ to $\leq 5\%$ increase, $> 5\%$ to $\leq 7\%$ increase, and $> 7\%$ increase. The number and percentage of subjects in each category will be summarized by visit.

Median (Q1, Q3) and mean (95% CI) of percentage change from baseline in observed hip and spine BMD over time will be plotted by treatment group. Listings of hip and spine DXA results will be provided.

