8.6.1. Key Secondary Safety Analyses

The percent change from baseline in hip and spine BMD at Week 48 will be analyzed using an ANOVA model. The model will include treatment group as fixed effect. The details are provided in the Statistical Analysis Plan (SAP).

The change from baseline in serum creatinine at Week 48 will be analyzed using an ANCOVA model with baseline serum creatinine as a covariate, and treatment group as a fixed effect. The details are provided in the SAP.

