1.1. Study Objectives

The primary objectives of this study are as follows:

- To compare the efficacy of TAF 25 mg versus TDF 300 mg once daily for the treatment of hepatitis B e antigen (HBeAg)-negative, CHB at Week 48 in treatment-naïve and treatment-experienced subjects. The primary efficacy parameter is the proportion of subjects with plasma HBV DNA levels below 29 IU/mL
- To compare the safety and tolerability of TAF 25 mg once daily versus TDF 300 mg once daily for the treatment of HBeAg-negative, CHB at Week 48 in treatment-naïve and treatment-experienced subjects

The key secondary safety objectives of this study are as follows:

- To compare the safety of TAF 25 mg once daily versus TDF 300 mg once daily as determined by the percent change from baseline in hip and spine bone mineral density (BMD) at Week 48
- To compare the safety of TAF 25 mg once daily versus TDF 300 mg once daily as determined by the change from baseline in serum creatinine at Week 48
- To compare the safety of TAF 25 mg once daily versus TDF 300 mg once daily as determined by treatment-emergent proteinuria through Week 48

Other secondary objectives of this study are as follows:

- To compare the efficacy of TAF 25 mg once daily versus TDF 300 mg once daily for the treatment of HBeAg-negative, CHB in regard to the proportion of subjects with plasma HBV DNA levels below 29 IU/mL at Week 96, and 144
- To compare the efficacy of TAF 25 mg once daily versus TDF 300 mg once daily for the treatment of HBeAg-negative, CHB in regard to the proportion of subjects with plasma HBV DNA levels below 29 IU/mL (target not detected) at Weeks 48, 96, and 144
- To compare the biochemical (alanine aminotransferase [ALT] normalization) response of TAF 25 mg once daily versus TDF 300 mg once daily for the treatment of HBeAg-negative, CHB at Weeks 48, 96, and 144
- To compare the serological response (loss of hepatitis B surface antigen [HBsAg] with seroconversion to antibody to HBsAg [anti-HBs]) of TAF 25 mg once daily versus TDF 300 mg once daily for the treatment of HBeAg-negative, CHB at Weeks 48, 96, and 144
- To compare the change in fibrosis as assessed by FibroTest[®] of TAF 25 mg once daily versus TDF 300 mg once daily for the treatment of HBeAg-negative, CHB at Weeks 48, 96, and 144
- To compare the incidence of drug resistant mutations of TAF 25 mg once daily versus TDF 300 mg once daily at Weeks 48, 96, and 144

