2. TYPE OF PLANNED ANALYSIS

The Week 48 analysis for Non-China subjects was already conducted after the last subject completed the Week 48 visit or prematurely discontinued study drug. This statistical analysis plan (SAP) describes the analysis plan for the Week 48 analysis of subjects enrolled in China only.

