7.4.2. Serum Creatinine

The baseline and change from baseline in serum creatinine at Week 48 will be summarized using descriptive statistics.

Missing values for serum creatinine will be imputed using LOCF up to Week 96 for the analyses of change from baseline in serum creatinine. The last on-treatment postbaseline observation will be carried forward to impute the missing value. Baseline observation will not be carried forward.

Change from baseline in observed serum creatinine will be analyzed similarly.

For all of the other renal safety analyses, observed creatinine values will be used.

Median (Q1, Q3) and mean (95% CI) of change from baseline in observed serum creatinine overtime will be plotted by treatment group.

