7.11. Changes From Protocol-Specified Safety Analyses

Treatment-emergent proteinuria was not included as a key secondary safety endpoint in protocol amendment 3.1 and is added in the SAP.

As no Ophthalmologic assessment was performed in China, no analysis will be conducted.

Comparison of the safety and tolerability of TAF versus TDF for the treatment of HBeAg-negative, CHB beyond Week 48 during the double-blind phase in treatment-naive and treatment-experienced subjects was not included as a secondary objective of this study and is added in the SAP.

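### The China Week 48 SAP keeps comparative bone and creatinine objectives but plans no TAF-TDF estimate or interval, and does not record that the protocol's models are not used

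*SAP*

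**What the plan says.** Protocol 8.6.1 (Key Secondary Safety Analyses) names the models and leaves details to the SAP.

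- **BMD:** "The percent change from baseline in hip and spine BMD at Week 48 will be analyzed using an ANOVA model". On its terms: "The model will include treatment group as fixed effect".
- **Creatinine:** "an ANCOVA model with baseline serum creatinine as a covariate, and treatment group as a fixed effect".

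Protocol 8.5.2 asks for a China analysis at Week 48 to see whether responses there are consistent with those in the overall population. It names no method.

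The SAP (section 2) "describes the analysis plan for the Week 48 analysis of subjects enrolled in China only". Its section 1.1 keeps the comparative objectives, for bone "as determined by the percent change from baseline in hip and spine bone mineral density (BMD) at Week 48", and likewise for creatinine. The methods are:

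- **SAP 7.3.1, BMD:** "Percentage change from baseline in hip BMD and spine BMD will be summarized by treatment group and visit using descriptive statistics", under LOCF and observed data, with status and category tables and by-arm plots.
- **SAP 7.4.2, creatinine:** "The baseline and change from baseline in serum creatinine at Week 48 will be summarized using descriptive statistics", again under LOCF and observed data, with by-arm plots.

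SAP 7.11 is the place for changes from the protocol's safety analyses. It records, for example, that "Treatment-emergent proteinuria was not included as a key secondary safety endpoint in protocol amendment 3.1 and is added in the SAP". It does not mention the ANOVA or the ANCOVA.

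**The concern.** The objectives are comparative but none of the planned outputs is. A reader of the China report would have a mean change in each arm and an interval around each mean, but no estimate of the treatment difference and no interval for it. Consistency of a treatment effect with the overall population cannot be judged without a China estimate of that effect and its uncertainty.

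The departure is also undeclared. Protocol 8.6.1 refers the reader to the SAP for the details of two models that the SAP does not contain. SAP 1.3 still recites the power of these comparisons (stating that it was calculated for non-China subjects), and SAP 7.11 lists other changes but not this one. Any difference computed later would be a choice made after the data were seen.

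**Working it through.** **1. What the SAP contains.** ANOVA and ANCOVA appear only in its list of abbreviations. In Appendix 1, Tables 48.1.1 to 48.2.2 (BMD) and 56.1 to 56.2 (creatinine) are by-visit summaries. Figures 11.2.1, 11.2.2 and 13.2 show by-arm means with 95% CIs. No table or figure gives a difference between arms. SAP 3.3 reclassifies the HBV DNA strata for a stratified analysis, but none is specified.

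**2. The plan's own figures.** Inputs from Protocol 8.8 and SAP 1.3:

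- allocation 260:130, two-sided alpha 0.025 (not restated for creatinine; assumed the same)
- hip: difference 1 point, SD 2.20
- spine: difference 1 point, SD 3.08
- creatinine: difference 0.03 mg/dL, SD 0.12

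Power = Φ(δ / [SD × √(1/260 + 1/130)] − 2.241), with √(1/260 + 1/130) = 0.1074.

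| Endpoint | δ/SE | Power | Stated |
|---|---|---|---|
| Hip | 4.23 | 97.7% | at least 90% |
| Spine | 3.02 | 78.3% | 77% |
| Creatinine | 2.33 | 53.4% | 52% |

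The stated values are supported, so the planning SDs can be carried to China.

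**3. Precision in China at 100/50, everyone measured.** Half-width = 1.96 × SD × √(1/100 + 1/50), with the root equal to 0.1732.

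| Endpoint | Half-width | Planned difference | Power at two-sided 0.05 (noncentral t) |
|---|---|---|---|
| Hip | 1.96 × 2.20 × 0.1732 = 0.75 points | 1 point | 74% |
| Spine | 1.96 × 3.08 × 0.1732 = 1.05 points | 1 point | 46% |
| Creatinine | 1.96 × 0.12 × 0.1732 = 0.041 mg/dL | 0.03 mg/dL | 30% |

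For spine and creatinine the half-width exceeds the planned difference.

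**4. Fewer scanned.** DXA is done only at capable China sites (SAP 3.1.6), and the number scanned is not given. At an assumed 60/30, √(1/60 + 1/30) = 0.2236 and the hip half-width is 1.96 × 2.20 × 0.2236 = 0.96 points.

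**5. By-arm intervals do not stand in for the difference.** Hip at 100/50: the TAF half-width is 1.96 × 2.20/√100 = 0.43 and the TDF half-width is 1.96 × 2.20/√50 = 0.61. The two intervals overlap for any difference below 0.43 + 0.61 = 1.04 points. The interval for the difference excludes zero above 0.75. At an observed difference of exactly 1 point the plots overlap, yet the interval for the difference runs from 0.25 to 1.75.

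**6. Adding baseline BMD.** The half-width is multiplied by √(1 − r²), where r is the correlation of baseline with percent change. The documents give no r. Over an assumed 0.1 to 0.5 the factor is 0.995 to 0.866, and the hip half-width at 100/50 goes from 0.75 to between 0.74 and 0.65.

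**The case against.** The strongest case for the SAP is its scope. It covers a local registration cohort that the power calculation excludes, and Protocol 8.5.2 names no method for it. With 74%, 46% and 30% power at best, formal tests would say little, and descriptive reporting runs through the whole SAP: the primary endpoint in 6.1.2 also gets only numbers and percentages. This stands as a reason not to test. It is not a reason to omit an estimate, because low precision makes the interval more useful. Nor does it explain the silence in 7.11, which does list the other changes made for this analysis.

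For BMD, a treatment-only ANOVA on two arms can be rebuilt by hand from n, mean and SD. That is true and limits the loss. It does not hold for the creatinine ANCOVA, and a reader should not have to derive the key contrasts.

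Three stronger readings are tempting, and the documents do not support them.

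- **That the models were dropped from the confirmatory analysis.** The non-China Week 48 analysis was already done, and its SAP is not available here.
- **That the scanned subset is small and probably imbalanced at baseline.** The number scanned is not given. DXA capability belongs to the site, and treatment was centrally randomised, so the subset remains a randomised comparison.
- **That the protocol's BMD model is biased because it omits baseline BMD and strata.** Omitting covariates from a randomised contrast costs precision, by an amount that depends on an unstated correlation. It does not bias the estimate.

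**Conclusion.** The point holds for the China Week 48 analysis. The objectives call for a comparison, the protocol supplies models, and the SAP provides only by-arm summaries and by-arm intervals without declaring the change. The consequence is a missing effect estimate and interval for three key secondary safety endpoints, not a wrong result.

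The half-widths of about 0.75 points (hip), 1.05 points (spine) and 0.041 mg/dL (creatinine) assume the planning SDs and complete measurement in 100 and 50 subjects. The 0.96 for hip assumes 60 and 30 scanned. They show that the China result would be an estimate with wide uncertainty and should be presented as one. The value of baseline BMD as a covariate is secondary and rests on an assumed correlation.

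**What to change.** In SAP 7.3.1 and 7.4.2, report the Week 48 TAF-TDF difference with its 95% CI, for both LOCF and observed data:

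- **Hip and spine BMD:** the protocol's treatment-only ANOVA, so that the estimate is comparable with an analysis under Protocol 8.6.1. Add an ANCOVA with baseline BMD for precision; the baseline value is non-missing by definition in the DXA sets (SAP 3.1.6.1 and 3.1.6.2).
- **Creatinine:** the protocol's ANCOVA with baseline creatinine.

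State that these are estimates without formal testing. Record in SAP 7.11 any departure from Protocol 8.6.1, including the added BMD ANCOVA. Randomisation strata may be added but are optional.

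The cost is SAP wording and ten estimates: two BMD sites × two models × two data handlings = 8, plus creatinine × two data handlings = 2. No new data, visits or procedures are needed.

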2.2. Week 48 Analysis (Primary Analysis)

The Week 48 analysis will be conducted after the last subject completes the Week 48 visit or prematurely discontinues study drug.

Further analyses after Week 48 will be conducted if warranted.

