3.5. Missing Data and Outliers

3.5.1. Missing Data

A missing datum for a given study analysis window may be due to any of the following reasons:

- A visit occurring in the window but data were not collected or were unusable
- A visit not occurring in the window
- A subject permanently discontinuing from the study before reaching the window

For the primary endpoint and the secondary efficacy endpoints involving proportions, missing data will be handled using M = F approach. Sensitivity analyses will also be performed including an analysis excluding all missing data.

For the 3 key secondary safety endpoints (percentage change from baseline in hip BMD at Week 48, percentage change from baseline in spine BMD at Week 48, change from baseline in serum creatinine at Week 48), an analysis will be performed using the last observation carried forward (LOCF) method to impute missing data.

For the remaining endpoints, values for missing data will not be imputed, unless specified otherwise.

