6. EFFICACY ANALYSES

For the Week 48 analyses, efficacy data will be summarized for the double-blind phase up to Week 96), with the exception that summaries using M = F approach will be presented up to Week 48 only. All efficacy data up to the Week 48 data-cut including data collected during open-label phase and 24-week treatment-free follow-up period will be listed.

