7. SAFETY ANALYSES

For Week 48 analysis, safety data will be summarized for the double-blind phase only up to Week 96. The upper limit of the least frequent schedule analysis window of Week 96 (Study Day 839) will be used as Week 96 data cut for cumulative summaries of safety events (eg, treatment-emergent AEs, treatment-emergent laboratory abnormalities). All safety data up to the Week 48 data-cut including data collected during the open-label phase and the 24-week treatment-free follow-up period will be included in data listings.

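### LOCF to Week 96 in the Week 48 analysis would fill in BMD and creatinine visits that subjects have not yet reached

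*SAP*

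**What the plan says.** SAP Section 2.2 sets the timing: "The Week 48 analysis will be conducted after the last subject completes the Week 48 visit or prematurely discontinues study drug". Section 7 sets the reach of the safety tables: "For Week 48 analysis, safety data will be summarized for the double-blind phase only up to Week 96".

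Within that reach, Section 7.3.1 imputes BMD ("Missing values for hip and spine BMD will be imputed using LOCF up to Week 96 for the analyses of percentage change from baseline") and Section 7.4.2 does the same for creatinine ("Missing values for serum creatinine will be imputed using LOCF up to Week 96 for the analyses of change from baseline in serum creatinine"). Both carry the last on-treatment postbaseline value; Section 7.3.1 puts it as "The last on-treatment postbaseline observation will be carried forward to impute the missing value". The only restriction in either section is that the baseline value is not carried. SAP Appendix 1 lists the outputs as by-visit LOCF tables: 48.1.1 (hip), 48.2.1 (spine) and 56.1 (creatinine).

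Among the reasons for a missing datum, Section 3.5.1 lists "A visit not occurring in the window". For efficacy, Section 6 also allows summaries to Week 96, but "summaries using M = F approach will be presented up to Week 48 only".

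**The concern.** LOCF is meant for a value that should exist and does not. Under SAP Section 1.2, all China subjects are enrolled under Amendment 3.1 and have about three years of double-blind treatment. A subject who has just passed Week 48 at the cut is therefore still on blinded drug, with Weeks 72 and 96 pending rather than lost. The LOCF sentences do not separate the two situations, and a programmer who follows them would copy the Week 48 value into both later visits.

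The affected columns would show an N close to the full analysis set while partly repeating earlier measurements. A reader could take the repetition for stability of bone density or creatinine after Week 48, in an analysis produced for local registration.

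**Working it through.** The documents give no figure to reproduce, so the check traces the rule and then sizes it.

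**Scope of LOCF elsewhere.** Protocol Section 8.2.2 and SAP Section 3.5.1 attach LOCF to the three key secondary safety endpoints, all at Week 48. SAP Section 7.4.2 itself opens with creatinine change at Week 48. The extension to Week 96 appears only in the two imputation sentences, and Section 7.11 does not list it as a change from the protocol.

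**Visits affected.** BMD: Weeks 72 and 96 (Table 3-4). Creatinine: Weeks 56, 64, 72, 80, 88 and 96 (Table 3-2). Week 48 is not affected, because at the cut every subject has reached Week 48 or discontinued.

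**Inputs for the size.** Window openings come from Tables 3-2 and 3-4: BMD Week 72 Day 420, Week 96 Day 588; creatinine Week 72 Day 476, Week 96 Day 644. Nominal days are 504 (Week 72) and 672 (Week 96). Assumptions: the cut is at the last subject's Day 336, accrual is uniform over A weeks, and dropout is ignored. The documents do not give A, so 26, 52 and 104 weeks are shown.

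**Formula.** Share of subjects with no possible record = min(1, (day − 336) / (7A)), where day is the window opening or the nominal day.

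| Visit and basis | Days beyond 336 | A = 26 | A = 52 | A = 104 |
|---|---|---|---|---|
| BMD Week 72, window opening | 84 | 46% | 23% | 12% |
| BMD Week 96, window opening | 252 | 100% | 69% | 35% |
| Creatinine Week 72, window opening | 140 | 77% | 38% | 19% |
| Creatinine Week 96, window opening | 308 | 100% | 85% | 42% |
| Week 72, nominal day | 168 | 92% | 46% | 23% |
| Week 96, nominal day | 336 | 100% | 92% | 46% |

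For example, BMD Week 96 at A = 52 is 252 / 364 = 69% by window opening and 336 / 364 = 92% by nominal day. The first counts only subjects who could not have any record in the window. The second is closer to what visits on schedule would give.

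**After the fix.** With LOCF stopped at Week 48, or limited as described under the fix, the share imputed only because a visit is not yet due is 0 at every visit.

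**The case against.** Three parts of the opposing case stand.

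- No key secondary endpoint is touched. A reader might infer that the three key secondary safety results are compromised, but they are defined at Week 48.
- The harm is contained. Every LOCF table has an observed-data companion (48.1.2, 48.2.2, 56.2). The BMD and creatinine plots, the BMD status and gradation tables and the other renal analyses use observed values. Sections 7.3.1 and 7.4.2 specify no between-arm test.
- The wording on missing data is not conclusive. Section 3.5.1 lists discontinuation before the window as a separate reason, so the phrase about a visit not occurring can be read as covering missed visits only. The SAP does not settle this, and a programmer might apply an unwritten exclusion. Equally, Section 6 gives no reason for stopping the M = F summaries at Week 48, so it cannot be said that the authors saw the same problem there.

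Two stronger readings are tempting but not supported.

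The first is that the later columns would be mainly Week 48 copies. At 52 weeks of accrual and nominal visits, 28/52 = 54% of subjects have reached Week 72, and Week 48 copies are 24/52 = 46% of each of the Week 72 and Week 96 BMD columns.

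The second is that the arm difference would be understated by a known amount. Suppose hip loss stays linear at the planning rates (−1.17% TDF, −0.17% TAF per 48 weeks) and A = 52. The mean last-scan time is then (24×48 + 24×72 + 4×96)/52 = 62.8 weeks. TDF at Week 96 would show −1.17 × 62.8/48 = −1.53% instead of −2.34%, and the difference 1.3 instead of 2.0 points. Linearity is an assumption, however. Protocol Section 1.3.2 reports, for one of the studies behind the planning figures, declines below 2% that occurred by Week 24 at the spine and Week 72 at the hip. If loss levels off in that way, carried-forward spine values are barely biased and the hip bias is smaller.

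**Conclusion.** The rule is wrong as written, with moderate severity. Followed literally, it puts carried-forward values into the post-Week 48 columns of Tables 48.1.1, 48.2.1 and 56.1 for subjects whose visits are still pending. This overstates N and could suggest a plateau. The conclusion rests on the text of Sections 2.2, 7.3.1 and 7.4.2 and on the absence of any exemption.

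The size is less certain. The Week 96 BMD shares of 35% to 100% by window opening, or 46% to 100% by nominal visit, depend on the assumed 26 to 104 weeks of uniform accrual and on a cut at the last subject's Day 336. Whether the arm difference is biased depends on whether loss continues after Week 48, which the documents do not establish.

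**What to change.** In Sections 7.3.1 and 7.4.2, change the limit of the LOCF imputation from Week 96 to Week 48, and present later visits as observed data only. This matches the protocol, SAP Section 3.5.1 and the Week 48 limit on M = F summaries in Section 6.

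If LOCF is wanted beyond Week 48, state that it applies only where the subject's window for that visit closed before the data cut, or the subject had already discontinued study drug, and record the extension in Section 7.11.

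The cost is two sentences and, for the second option, one programming filter. No data are lost, the observed-data tables are already planned, and the Week 48 LOCF results do not change.
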